5. STUDY INTERVENTIONS

5.1 Interventions, Administration, and Duration

The intervention in this study is Mindful Awareness in Body-oriented Therapy (MABT), administered one-on-one by therapists trained in the MABT protocol at the outpatient treatment site where the participant was recruited from and receives their MAT care. Individuals in the MABT intervention group will receive 8 weekly 1.25 hour one-on-one sessions of MABT between baseline and the 3 month follow-up assessment. There are no restrictions to supportive care, medications, or other treatments which intervention group participants may use during their participation in the study with the exception of additional manual (e.g., massage) and/or mind-body therapies of meditation and yoga during the first three months of study engagement (this information is part of the screening process for enrollment, and will be reiterated by the research coordinator at the time of study enrollment). There are no anticipated adverse effects of the intervention other than the possibility of short-term emotional discomfort.

At six months, those in the MABT treatment group with continued substance use will be offered an additional six sessions of MABT between the 6 month and 9 month assessments.

5.2 Handling of Study Interventions

Mindful Awareness in Body-oriented Therapy (MABT): The MABT intervention has a well-developed protocol and training manual for research. Used in multiple clinical trials,[83, 85, 86, 93-95] the protocol has an incremental approach for teaching interoceptive awareness skills and developing weekly individualized homework based on session content to promote integration of practice into daily life. Individuals in the MABT treatment group will receive 8 weekly 1.25 hour one-on-one sessions of MABT. Research therapists will be hired and trained to provide the MABT intervention. MABT has three distinct stages (see Table 2). Stage 1 (sessions 1-2), develops body literacy, the ability to identify and articulate sensory awareness. Body literacy training is done in the context of massage therapy to facilitate sensory awareness related to attention to the quality of soft tissue (e.g., muscular tension). Stage 2 (sessions 3-4) focus on interoceptive awareness training to develop the ability to access inner body awareness and begin to make links between physical and emotional sensations. Stage 3 (sessions 5-8) focuses on the development and practice of mindful body awareness involving sustained interoceptive attention which facilitates positive shifts in sensory experience as well as insights that motivate behavior change. Each session begins with a semi-structured check-in to build trust and familiarity between therapist and participant, and ends with session review to facilitate cognitive integration of the session

material and to collaboratively develop the homework for the interim week. The interoceptive training components (stages 1-3) are designed with an incremental approach to facilitate learning, particularly important for individuals with SUD who often have difficulties attending to sensory (physical and emotional) awareness. Individualized homework is based on session content and crafted to promote integration of practice into daily life.

The additional six MABT sessions that will be offered to eligible participants at 6 months will be delivered as explained above and will include all stages of the intervention as outlined in Table 2 but will be individualized to address the intervention components needing the most review (if the participant did not complete MABT initially) or will follow the intervention protocol for delivery of the first 6 of 8 sessions if the received no prior MABT sessions when initially assigned.

A single therapist works with each study participant for MABT delivery. In case of illness or vacation, on the part of either participant or interventionist, the intervention period allows for approximately 12 weeks to deliver an 8 week intervention. Any longer-term breaks needed in interventionist coverage/ staff turnover will be handled by having a trained therapist ready to step-in if needed, either to provide temporary coverage (i.e. to work with one set of 3-4 participants over 2-3 months to deliver a full set of MABT sessions) or to join the research team more permanently.

Treatment As Usual: All participants will continue to receive usual outpatient treatment at the site from which they were recruited. The outpatient programs at these sites are comparable; they offer medication treatment provided by a Medical Provider or through a Nurse Care Manager (NCM) model adapted from the Massachusetts Model as piloted in the MAT-PDOA program. The model uses Nurse Care Managers (NCM) as the hub of the medical care team to coordinate and manage patients. The use of the NCM addresses many barriers to medication prescribing that physicians face. For example, treatment for opioid use disorders with buprenorphine/naloxone (BUP/NX) is time-intensive in the first 2-3 months. Clinical steps which the NCM assists include: an initial screening for the appropriateness of BUP/NX; a comprehensive assessment of substance use and consequences, medical and mental health, and current barriers to and supports for recovery; review for formal diagnosis of opioid use disorder and appropriateness for MAT; scheduling and monitoring of the induction (i.e., initiation of BUP/NX which must be accomplished while patients are in withdrawal), followed by weekly visits for prescriptions, and urine drug testing for the first 1-2 months (less frequent thereafter if patients are abstaining). Frequent team meetings with the physician, NCM and program manager occur, during which team members can monitor progress and update treatment plans together. Counseling is available for all patients, but not required.

5.3 Concomitant Interventions

5.3.1 Allowed Interventions

Participants will all be enrolled in MAT for the duration of the study. Participants are welcome to engage in optional counseling or attend peer support meetings such as 12-step groups, as this is considered part of treatment as usual (TAU). If a participant withdraws

from MAT during the study, we will continue to follow them (per intent to treat); in all cases, we will collect information on any related treatment activities engaged in during the study period.

5.3.2 Required Interventions

The participants must have received their fourth weekly MAT prescription to be enrolled in the study. Per intent-to-treat design, study participation is not contingent on continued adherence to MAT treatment once enrolled in the study.

5.3.3 Prohibited Interventions

There are no restrictions to supportive care, medications, or other treatments which participants may use during their participation in the study with the exception of additional manual (e.g., massage) and mind-body therapies (specifically yoga and meditation) from baseline to 3 months. To assess whether participants adhere to this exclusion, or utilize these therapies later in the study, participants will be asked about their receipt of massage or participation in any yoga or meditation classes at each assessment.

5.4 Adherence Assessment

To assess adherence to the study intervention we will record number of sessions attended. In addition to an intent-to-treat analysis, we will also examine MABT dose. Specifically, we will examine outcomes for participants who attended > 75% of the initial intervention sessions (i.e. 6-8 sessions) between baseline and 3 months, as this is the number of sessions needed in order to receive all intervention components, compared to TAU. We will also record the number of additional sessions received by eligible participants between 6 and 9 months.

6. STUDY PROCEDURES

6.1 Table 4. Schedule of Evaluations

Assessment	Screening: Visit or Call (Day-14 to Day -1)	Baseline, Enrollment, Randomization: Visit 1 (Day 0)	Treatment Visit 1 (W1)	Treatment Visit 2-8 (W2 - 11)	Followup 1: Post-Treatment Visit (W12)	Followup2: Visit (W24)	Booster Treatment Visits 1-6 (W25 - 38)	Followup2: Visit (W39)	Followup2: Visit (W52)
Screening Questions	X								
Inclusion/Exclusion Criteria	X								
Informed Consent Form		X							
Demographics and Health History		X							
Trauma History (TLEQ)		X							
REDCap Survey		X			X	X		X	X
Treatment Adherence (Retention to MAT)						X			X

Assessment	Screening: Visit or Call (Day -14 to Day -1)	Baseline, Enrollment, Randomization: Visit 1 (Day 0)	Treatment Visit 1 (W1)	Treatment Visit 2-8 (W2 - 11)	Followup1: Post-Treatment Visit (W12)	Followup2: Visit (W24)	Booster Treatment Visits 1-6 (W25 - 38)	Followup2: Visit (W39)	Followup2: Visit (W52)
Economic Indicators (Employment, Health Utilization, Legal Status)		X			X	X		X	X
Toxicology screen		X							
Enrollment/Randomization		X			X	X		X	X
MABT Process Evaluation			X	X			X		
Adverse Events			X	X	X	X	X	X	X

6.2 Description of Evaluations

6.2.1 Screening Evaluation

Consenting Procedure

The Research Coordinator (RC) at each site will acquire verbal consent to ask screening questions to determine eligibility prior to beginning screening procedures. Written consent will be obtained for all further study procedures as described in section 6.2.2.

Screening

After acquiring consent to screen, the RC at each site will screen interested patients to determine eligibility in-person at the time of referral (if available) or by phone using a standardized screening script. On conclusion, the results of screening interview will be entered into the screening log of the study database. Results are 1) eligibility based on inclusion/exclusion criteria, 2) if eligible, election of participation (if no, reason why not), 3) if not eligible, reason for ineligibility. Candidates who are eligible and willing to continue will be scheduled for the consent /initial assessment visit within 14 days of the screening, or be rescreened prior to progressing. Eligibility, election, and follow-up information (for those who are eligible and willing to continue) will be entered in the study database.

6.2.2 Enrollment, Baseline, and/or Randomization

Enrollment

The first study visit will begin with the consent process. At the consent visit, the RC will ask if the candidate would like to read it themselves or have it read to them, then will give the participant time to read the consent (or read it aloud). Then the RC will paraphrase each section of the consent form, and encourage the candidate to ask questions. If the candidate wishes to proceed, they will sign and date the consent form. If there is any concern about comprehension, the RC will administer an adapted 7-item Mini-Mental Status Exam to ensure that there is not cognitive impairment.

The RC will also explain the HIPAA and Medical Records Release forms (if required by the clinical site) to acquire limited data elements from the candidate's medical record. Permission to access medical records is required for participation in the research study. A copy of the forms will be provided to the candidate. A locator form with additional contact information will also be requested, but refusal does not preclude participation in the study.

After informed consent is given, the baseline assessment is completed. On completion of the baseline assessment, the participant will be enrolled and randomized.

Completion status for the consent procedures will be entered in the study database, and signed forms filed in the candidate's name file in a locked filing cabinet, separate from numerical identifiers.

Baseline Assessments

The baseline assessment requires the participant to complete: 1) the Timeline Follow-back Interview to report on substance use over the past 90 days, 2) an online survey (REDCap) to collect a set of baseline-only questionnaires specific to demographics and health history, 3) an online survey using REDCap that collect responses to self-report outcome measures, 4) a toxicology screen involving a urine sample for biochemical evaluation. The administration of the baseline assessment is process takes approximately 1 hour. All assessments will be delivered in a standardized order as outlined below; at baseline only, there are two additional measures on the online REDCap survey

Should a participant be unable to provide data during the scheduled assessment (e.g., unable to provide a urine sample, or unable to complete the assessment in one sitting), research coordinators have up to 14 days to complete the data collection for the assessment.

Baseline, Enrollment, Randomization: Visit 1 (Day 0)

Measures:

Primary outcome:

- Time-Line Follow-Back Interview (TLFB)[3, 4] will be used to assess self-reported opioid use, and use of other illicit drugs, marijuana and alcohol use.

Demographics and health history:

- Health History Form is based on the Addiction Severity Index.[1]
- Trauma Life Events Questionnaire (TLEQ)[2] will be used to describe lifetime trauma exposure.

Secondary outcomes:

- The PHQ-9 will be used to measure depression symptoms.[6, 7].
- The GAD-7 will be used to measure anxiety symptoms.[8]
- Posttraumatic Stress Disorder Checklist for DSM-5 (PCL-5),[9] assesses symptoms of post-traumatic stress on a Likert-type scale.

- Difficulty in Emotion Regulation Scale - short form (DERS- SF)[10] assesses difficulties in the modulation of emotional arousal.
- Opioid craving will be assessed using a single item numeric scale.[5] Participants are asked: “On a scale of 0-10, please indicate how much craving you have experienced during the past week,” with responses anchored at “0=no craving at all” and “10-strongest craving ever”.
- Freiberg Mindfulness Questionnaire has 14 items to assess skills learned in the intervention.[14]
- Multidimensional Assessment of Interoceptive Awareness (MAIA)[15] has 32 items on a Likert-type scale to assess skills learned in the intervention.
- Brief Pain Inventory (BPI) is a validated, widely used measurement tool for assessing clinical pain.[18] The BPI will be supplemented with a single question on duration of currently reported pain in order to establish whether the pain is acute or chronic.
- Medical Symptoms Checklist will assess self-report of physical symptoms.[19]

Descriptive Data:

- Economic Indicators questions will gather data on employment, health utilization, and legal status.
- Toxicology screen will be used to collect point prevalence for substance use on at each assessment time point, and will serve as supplemental data for validation of the TLFB results.

After the completion of the baseline assessment, the participant is formally enrolled in the study.

Randomization

Following baseline data collection, participants will be randomized to treatment group by the Research Coordinator. Randomization will be provided by the project statistician. Stratified randomization by study site, baseline self-reported chronic pain, and gender, will be used to distribute participants evenly between the two treatment conditions at each facility and within each gender and experience of chronic pain. Randomization will use a modified minimization method algorithm[96] based on an overall imbalance score which measures how far out of balance (within strata) the study is for a given set of random assignments to ensure approximately equal accrual into the two experimental arms and to facilitate concealment of treatment assignments. After randomization (for those assigned to treatment group), the RC will contact the site interventionist to inform them of their new assigned participant to schedule the first intervention visit.

6.2.3 Blinding

The statistician will be blind to study group. The RC at each facility will not be blind to condition and will inform participants of their study group condition.

6.2.4 Follow-up Visits

Treatment

Initial Treatment Visit 1 (W1)

- Adverse Events
- MABT Process Evaluation (self-report by interventionists)

Initial Treatment Visit 2-8 (W2 - 11)

- Adverse Events
- MABT Process Evaluation (self-report by interventionists)
- MABT Practice Log (self-reported home practice by participants for use by interventionists)

Additional MABT Sessions 1-6 (W25 - W38)

- Adverse Events
- MABT Process Evaluation (self-report by interventionists)
- MABT Practice Log (self-reported home practice by participants for use by interventionists)

Assessments

Followup1-4 Assessment Visits (W12, W24, W39)

The follow-up assessments will be scheduled 12 weeks, 24 weeks, and 39 weeks from baseline, and takes approximately 45 minutes to complete. Coordinators will make every effort to schedule the assessment near to the target date, but are allowed -2 weeks/+4 weeks to capture follow-up assessment data. In addition to this assessment, we will also gather treatment retention data through electronic medical record (EMR) at the 6 and 12 month assessments.

Should a participant be unable to provide data during the scheduled assessment (e.g., unable to provide a urine sample, or unable to complete the assessment in one sitting), research coordinators have up to 14 days to complete the data collection for the assessment.

W24: The Time-Line Follow-Back Interview (TLFB)[3, 4] results collected at 6 months will be used to determine those in the MABT study group with continued substance use who will be offered six additional MABT sessions between month 6 and 9. Criteria for eligibility for additional MABT sessions is 1) randomized to the MABT + TAU study group, and b) self-report of substance use on the TLFB, including any days of heavy alcohol drinking and excluding marijuana use.

Primary outcome:

- Time-Line Follow-Back Interview (TLFB)[3, 4] will be used to assess self-reported opioid use, and use of other illicit drugs, marijuana, and alcohol.

Secondary outcomes:

- The PHQ-9 will be used to measure depression symptoms.[6, 7].
- The GAD-7 will be used to measure anxiety symptoms.[8]
- Posttraumatic Stress Disorder Checklist for DSM-5 (PCL-5),[9] assesses symptoms of post-traumatic stress on a Likert-type scale.
- Difficulty in Emotion Regulation Scale - short form (DERS- SF)[10] assesses difficulties in the modulation of emotional arousal.
- Opioid craving will be assessed using a single item numeric scale.[5] Participants are asked: “On a scale of 0-10, please indicate how much craving you have experienced during the past week,” with responses anchored at “0=no craving at all” and “10-strongest craving ever”.
- Freiberg Mindfulness Questionnaire has 14 items to assess skills learned in the intervention.[14]
- Multidimensional Assessment of Interoceptive Awareness (MAIA)[15] has 32 items on a Likert-type scale to assess skills learned in the intervention.
- Brief Pain Inventory (BPI) is a validated, widely used measurement tool for assessing clinical pain.[18] The BPI will be supplemented with a single question on duration of currently reported pain in order to establish whether the pain is acute or chronic.
- Medical Symptoms Checklist will assess self-report of physical symptoms.[19]

Descriptive Data:

- Economic Indicators questions will gather data on employment, health utilization, and legal status.
- Biochemical drug screen will be used to collect point prevalence for substance use on at each assessment time point, and will serve as supplemental data for validation of the TLFB results.
- Adverse Events

6.2.5 Completion/Final Evaluation

Followup2: Final Visit (W24)

The final evaluation (12 month follow-up) will be scheduled 52 weeks from baseline, and takes approximately 45 minutes to complete. Coordinators will make every effort to schedule the assessment near to the target date, but are allowed -2 weeks/+4 weeks to capture final assessment data. In addition, to this assessment, we will also gather treatment retention data through electronic medical record (EMR).

Should a participant be unable to provide data during the scheduled assessment (e.g., unable to provide a urine sample, or unable to complete the assessment in one sitting), research coordinators have up to two weeks to complete the data collection for the assessment.

If study staff learn of special circumstances that would necessitate collecting W24 data earlier than the allowed window of -2 weeks (e.g., expected relocation, incarceration, etc.), the

assessment will be completed early and the participant followed to determine if a repeat assessment within the allowable window is possible. If so, the final assessment will be repeated and the later data used in the final analysis. Participants will be remunerated for the second W24 assessment.

Primary outcome:

- Time-Line Follow-Back Interview (TLFB)[3, 4] will be used to assess self-reported opioid use, and use of other illicit drugs, marijuana, and alcohol.

Secondary outcomes:

- The PHQ-9 will be used to measure depression symptoms.[6, 7].
- The GAD-7 will be used to measure anxiety symptoms.[8]
- Posttraumatic Stress Disorder Checklist for DSM-5 (PCL-5),[9] assesses symptoms of post-traumatic stress on a Likert-type scale.
- Difficulty in Emotion Regulation Scale - short form (DERS- SF)[10] assesses difficulties in the modulation of emotional arousal.
- Opioid craving will be assessed using a single item numeric scale.[5] Participants are asked: “On a scale of 0-10, please indicate how much craving you have experienced during the past week,” with responses anchored at “0=no craving at all” and “10-strongest craving ever”.
- Freiberg Mindfulness Questionnaire has 14 items to assess skills learned in the intervention.[14]
- Multidimensional Assessment of Interoceptive Awareness (MAIA)[15] has 32 items on a Likert-type scale to assess skills learned in the intervention.
- Brief Pain Inventory (BPI) is a validated, widely used measurement tool for assessing clinical pain.[18] The BPI will be supplemented with a single question on duration of currently reported pain in order to establish whether the pain is acute or chronic.
- Medical Symptoms Checklist will assess self-report of physical symptoms.[19]

Descriptive Data:

- Economic Indicators questions will gather data on employment, health utilization, and legal status.
- Biochemical drug screen will be used to collect point prevalence for substance use on at each assessment time point, and will serve as supplemental data for validation of the TLFB results.
- Adverse Events

Withdrawal of Participants

MABT sessions will be discontinued for any of the following three reasons, but not withdrawn from study (e.g., participant will be continued to be followed for study assessments):

1. Participants are inebriated or high from alcohol or drugs such that they are not able to engage in the intervention on more than one scheduled session.
2. If, in consultation with the participant's healthcare providers, there is concern for his/her safety and well-being (e.g., escalation of symptoms).

A participant could be withdrawn from study if:

If, in consultation with the participant's health care providers, there is sufficient concern for his/her safety and well-being that the participant may be withdrawn and re-directed to more appropriate care. This is described to the participant in the consent process.

If a participant chooses to formally withdraw from the study by notifying the principal investigator, any data collected from the participant will not be used in the analysis.

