7. SAFETY ASSESSMENTS

7.1 Specification of Safety Parameters

It is possible that participants may experience anxiety related to questions asked on the questionnaires. For participants who receive MABT, there may be anxiety due to the use of touch in the MABT sessions or the development of a new therapeutic relationship. During the course of the study, interventionists may develop concerns regarding a participant's risk of suicide or harm to self or others, or health concerns such as increased medical symptoms such as pain, or mental health symptoms of severe depression, anxiety, PTSD. Upon entering the study, all participants will be asked to sign a Treatment Information Release Form, which will allow for two-way communication between research and clinical staff to discuss concerns such as those described.

Any medical emergencies, disclosed suicidal ideation, or other urgent concerns for participant safety experienced by the research coordinators or interventionists will be addressed according to the procedures at the clinical site where the participant is seen. Review of these protocols and accessing emergency contact information will be included in the staff training for all study staff. The study staff with the experience will report the event and resolution/follow-up to the principal investigator(s) that day.

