8. INTERVENTION DISCONTINUATION

MABT sessions will be discontinued for any of the following reasons, but participant will not be withdrawn from study:

1. Participants are inebriated or high from alcohol or drugs such that they are not able to engage in the intervention on more than one scheduled session.
2. If, in consultation with the participant's healthcare providers, there is concern for his/her safety and well-being (e.g., escalation of symptoms).

The participant could be withdrawn from study if, in consultation with the participant's health care providers, there is sufficient concern for his/her safety and well-being that the

participant may be withdrawn and re-directed to more appropriate care. This is described to the participant in the consent process.

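### Withdrawal from the study on safety grounds appears to end outcome follow-up for participants who are deteriorating, and the plan does not say that assessments continue

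*Combined protocol and SAP*

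**What the plan says.** The Withdrawal of Participants text in Section 6.2.5 sets out two tiers, and Section 8 repeats them.

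- **Sessions only.** MABT sessions stop if the participant is repeatedly too intoxicated to take part, or if there is concern for safety (escalating symptoms are the example) after consulting providers. The participant stays in the study, which Section 6.2.5 explains as: "participant will be continued to be followed for study assessments".
- **Whole study.** Again after consulting providers, a participant may leave the study if "there is sufficient concern for his/her safety and well-being that the participant may be withdrawn and re-directed to more appropriate care". Section 8 opens the same rule with "The participant could be withdrawn from study if". Neither section gives a threshold separating the tiers or mentions any later assessment.

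A participant's own formal withdrawal is a separate case. Only there does the plan say that "any data collected from the participant will not be used in the analysis".

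On who raises safety concerns, Section 7.1 says "interventionists may develop concerns regarding a participant". It lists risk of self-harm or harm to others, increased symptoms such as pain, and severe depression, anxiety or PTSD symptoms. It also covers urgent concerns met by research coordinators.

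On intent to treat, Section 5.3.2 says "Per intent-to-treat design, study participation is not contingent on continued adherence to MAT treatment once enrolled in the study", Section 5.3.1 keeps following people who leave MAT, and Section 9.3 puts everyone enrolled into the ITT analysis.

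**The concern.** A participant can leave outcome follow-up because staff judge that he or she is doing badly. The problems that prompt such a judgement in Section 7.1 are largely those measured as secondary outcomes in Section 1.2 (depression, anxiety, trauma symptoms, pain). Missingness of that kind is informative. Counting the person in the ITT population does not supply outcomes that nobody collected.

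The two arms are not observed alike. Only MABT participants meet an interventionist, and only they can be moved to a session-only step. If use of the rule differs by arm, the comparison is biased. Section 9.2 expects loss not to differ by arm, but nothing in this rule protects that expectation. Section 7.6 says annual report tables are pooled over arms, so an imbalance would not show there. Adverse events are also solicited at follow-up visits (Section 7.3), so ending those visits thins safety data on the participants of most concern.

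**Working it through.** **1. The plan's own figure.** Section 9.2 expects 20% loss: 330 × (1 − 0.20) = 264, or 132 per arm, as stated. That is 165 × 0.20 = 33 lost per arm. No part of it is attributed to staff-initiated withdrawal.

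**2. Does follow-up stop?** Section 6.2.5 explains remaining in the study as continuing assessments. The higher tier is the alternative to remaining in the study and carries no provision for assessments. Stopping them is the natural reading, but it is an inference. Section 6.2.5 says the rule is described at consent; the consent text is not in the public document, so it cannot settle the matter.

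**3. Exposure by arm.**

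| | MABT + TAU | TAU |
|---|---|---|
| Coordinator follow-up assessments (12, 24, 39, 52 weeks) | 4 | 4 |
| Clinic provider or nurse care manager | yes | yes |
| Interventionist sessions | 8, up to 8 + 6 = 14 | 0 |
| Session-only step available | yes | no |

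More contact could produce more withdrawals in MABT. Having no intermediate step could produce more in TAU. The documents do not say which dominates.

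**4. Illustrative shift in one arm's observed mean.** With arm mean *m*, fraction withdrawn *f* and mean *w* among those withdrawn:

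shift = (*m* − *f·w*)/(1 − *f*) − *m* = *f*(*m* − *w*)/(1 − *f*)

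The values of *m* are the prior study's 12-month results quoted in Section 9.2 (88.6% MABT, 80.0% TAU; difference 8.6 points). *f* and *w* are assumptions with no source in the documents. On 165 people, 3% is about 5 and 5% about 8.

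| Arm losing people | *f* | *w* = 30% | *w* = 50% |
|---|---|---|---|
| MABT only | 3% | 0.03 × 0.586/0.97 = 1.8 points | 0.03 × 0.386/0.97 = 1.2 points |
| MABT only | 5% | 0.05 × 0.586/0.95 = 3.1 points | 0.05 × 0.386/0.95 = 2.0 points |
| TAU only | 3% | 0.03 × 0.500/0.97 = 1.5 points | 0.03 × 0.300/0.97 = 0.9 points |
| TAU only | 5% | 0.05 × 0.500/0.95 = 2.6 points | 0.05 × 0.300/0.95 = 1.6 points |

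Losses in MABT only would flatter MABT. Losses in TAU only would hide part of a real effect.

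**5. Both arms losing people, no true effect.** Take *m* = 80% in each arm (assumed) and subtract the TAU shift from the MABT shift, with *w* from 60% down to 0%:

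- 5% vs 0%: 0.05 × 0.20/0.95 = 1.1 points to 0.05 × 0.80/0.95 = 4.2 points.
- 5% vs 2%: 0.6 to 2.6 points.
- 5% vs 5% with the same *w*: 0.

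The bias needs an imbalance in rates or in the outcomes of those withdrawn. If outcomes are still collected from everyone, *f* = 0 and it vanishes.

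**The case against.** Several points on the other side stand.

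- The rule is permissive, graded above the session-only tier, and requires provider consultation. It is not unfettered staff discretion.
- The reason for stopping most closely tied to substance use, repeated intoxication at sessions, expressly keeps follow-up. The link to the primary outcome is therefore indirect.
- Data gathered before a staff withdrawal are not said to be discarded, so they would enter the repeated-measures model. The table in step 4 is a complete-case calculation and ignores them.
- Section 7.2 expects few or no study-related adverse events, so the rule may rarely be used.
- Section 7.1 recognises that the questionnaires may themselves cause anxiety, so ending assessments can sometimes be protective.
- Section 9.2 plans missing-data sensitivity analyses, with multiple imputation and pattern-mixture models under consideration. These can test assumptions about unseen outcomes, but they do not recover them, and none is fixed for this reason for loss.

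A reader might also infer that the rule contradicts Section 5.3. It does not do so literally: Sections 5.3.1 and 5.3.2 deal with leaving or not adhering to MAT. What it departs from is the principle behind them and behind Section 9.3.

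**Conclusion.** The concern holds as a gap in the follow-up rules. Sections 6.2.5 and 8 permit study-level withdrawal for safety and, on their natural reading, let outcome collection lapse for participants who are deteriorating. Any such loss is related to outcome, most directly for mental health and pain.

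A stronger reading is that the rule makes MABT look better. The documents do not support that: coordinators and clinic providers see both arms, TAU lacks the session-only step, and nothing shows how often either arm would be affected. The direction is open.

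The size is unknown. The shift of about 1 to 3 points, against 8.6 in the prior study, rests on assumed rates of 3-5%, assumed abstinence of 30-50% among those withdrawn, losses in one arm only and a complete-case mean. With few withdrawals, or equal rates and similar outcomes in both arms, the between-arm bias would be small or nil. The case for a change rests on its low cost and on the fact that uncollected outcomes cannot be restored later.

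**What to change.** Leave the clinical decision and the redirection to care as they are. Put the same text in Sections 6.2.5 and 8, for example:

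> *Redirection to other care does not by itself end outcome follow-up. TLFB and survey assessments continue where the participant is willing and the assessments are not themselves the safety concern. Retention data are still extracted from the medical record. Follow-up ends if the participant withdraws consent.*

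Record each staff-initiated withdrawal with date and reason, and report the counts by arm and reason with the trial results. In the same edit, reconcile the list in Section 6.2.5, which announces three reasons for stopping sessions but gives two.

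The cost is one short paragraph in two sections, a notice to staff and a few extra assessments by existing coordinators. Because the rule is described at consent, a small consent or IRB amendment may also be needed.
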